#### **9.4.1.2. Missing Data Handling**

No imputation for missing efficacy and safety data.

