2.3. Exploratory Endpoints

- Changes from baseline in Marsh-Oberhuber score assessed via EGD with biopsy after 2-week GC.
- The biopsy will be performed at screening and Day 29, or ET visit. Baseline is the last non-missing Marsh-Oberhuber score at screening.
- CSDS

- CDSD is a patient reported outcome (PRO) questionnaire collected daily. The version 2.1 includes 5 severity items and 3 frequency supplement questions (see [Appendix 2.2](#)) that will be collected daily.
 - CDSD Total Score is the sum of all 5 severity items. The CDSD Weekly Average Total Score will be calculated , for details on the calculation see below, Section [5.3.2](#) and [Appendix 2.2](#).
 - The CDSD Gastrointestinal (GI) Domain Score is the sum of items 1-4. The CDSD Weekly Average Gastrointestinal (GI) Domain Score will be calculated, for details on the calculation see below, Section [5.3.2](#) and [Appendix 2.2](#) .
 - For CDSD Nausea score and vomiting frequency, in addition to weekly average score, 3-day average will be derived as well (every 3 days start from Day 15 GC until Day 41). If 2 observations are missing, the 3-day average score will not be calculated. Day 15 Nausea score and vomiting frequency will be analyzed as well.
- For CDSD Total score, GI Domain score, individual severity item and frequency supplement question, the Baseline value is the average of most recent 7-day interval scores before Day 1 (not include Day 1) with at least 4 days with non-missing scores, and will be used as the baseline to calculate the change from baseline to the 1-day, 3-day average and weekly average. If there are ≥ 4 days missing scores in any 7-day interval before Day 1, the baseline value is set as missing.
- For post-baseline weekly average score calculation, Week 1 is from Day 1 to Day 7, Week 2 is from Day 8 to the day before Day 15 GC, Week 3 is from the day after Day 15 GC to Day 21. The number of days for Week 2 and Week 3 maybe equal to, less than, or greater than 7. See Section [5.3.2](#) for the details. The weekly average score is the weekly sum score divided by the number of days with non-missing in that week. If daily scores are missing for more than half of total days in a specific week, the average score is missing for that week.
- Change from baseline at each timepoint = observed (or derived as described above) value at each timepoint – baseline.
- The observed value and the change in PGIS

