3. ANALYSIS SETS

For purposes of analysis, the following analysis sets are defined:

Analysis Set	Description
Enrolled	All participants who sign the ICD.
Biomarker Analysis Set (BAS)	All participants who are randomly assigned to study intervention, receive any portion of study intervention, and have completed the GC on Day 15, without prohibited medications. Participants will be analyzed according to the intervention they are randomized.
Full analysis set (FAS)	All participants who are randomly assigned to study intervention, receive all 3 doses of study intervention, and complete at least 7 days of the 2-week GC without prohibited medications. Participants will be analyzed according to the intervention they are randomized.

Analysis Set	Description
Per protocol set (PPS)	The PPS will include all participants from the FAS who complete all 14 days of the 2-week GC and biopsies, and without major protocol violations that might affect the evaluation of the effect of study intervention on the primary endpoint. The PPS will be used in sensitivity analyses of the primary and secondary endpoints. Specific reasons for warranting exclusion from this population will be documented prior to database lock.
Safety analysis set (SAS)	All participants who receive any portion of study intervention. Participants will be analyzed according to the intervention they actually received.
PK analysis set (PKAS)	All participants who receive any portion of study intervention and have at least one concentration value.

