4.2.1. Analyses for Continuous Endpoints

For continuous endpoints, the change from baseline will be analyzed by timepoint using analysis of covariance (ANCOVA) model with treatment as a factor, baseline as a covariate. For endpoints without baseline, analysis of variance (ANOVA) model with treatment as a factor will be used for the analysis. Comparison of KAN-101 to PBO (providing LSM of the treatments, LSM of the treatment difference, p-value and 95% CI) will be generated.

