4.3. Methods to Manage Missing Data

If a PK concentration value is below Lower Limit of Quantification (LLOQ), that concentration value will be treated as 0 for all analysis. For IL-2, values below LLOQ will be treated as $\frac{1}{2}$ LLOQ. Other missing values will not be imputed for safety, efficacy and PK endpoints.

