5. ANALYSES AND SUMMARIES

In general, observed values and change from baseline (where applicable) will be descriptively summarized by treatment group with number of observations, mean, SD, min, 1st, 2nd (median) and 3rd quartiles, and max, unless otherwise specified. For log-transformed values the geometric mean and 95% CI will be presented with the summary statistics.

Data will be summarized and analyzed by treatment group for the main population of interest and a separate sensitivity/supplementary analysis(ses) based on the chosen analysis set from Section 3).

Endpoint	Analysis Set Applied for Main Analysis	Analysis Set Applied for Sensitivity/Supplementary Analysis
Biopsy (Vh:Cd, IEL Density Marsh-Oberhuber Score)	Full Analysis Set	Per Protocol Set and Safety Analysis Set
Biomarker (IL2)	Biomarker Analysis Set	Per Protocol Set and Safety Analysis Set
PK	PK Analysis Set	N/A
PRO (CDS, PGIS, PGIC)	Full Analysis Set	N/A
Demography and Safety	Safety Analysis Set	N/A
ADA	Safety Analysis Set	N/A

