5.3.2. CDSD

The weekly average score of each severity item and frequency question of CDSD (Diarrhea, Abdominal Pain, Bloating, Nausea, Number of times Vomiting, Tiredness, Number of Bowel Movements and Number of events of Diarrhea) as well as the weekly average CDSD Total Score, weekly average CDSD GI Domain Score (see [Section 2.3](#) and [Appendix 2.2](#)) and change from baseline will be descriptively summarized as stated in Section 5 for each treatment group by timepoint.

The change from baseline for weekly average of each of the 5 severity items and 3 frequency questions, the weekly average CDSD Total Score, and the weekly average CDSD GI Domain Score will be analyzed using ANCOVA models in [Section 4.2.1](#) by timepoint. LSM of the treatments with 95% CI, LSM of the treatment difference with PBO, p-value and 95% CI will be generated.

If there are multiple records on a same day, the earliest one will be used for analysis.

The analysis set(s) used for these endpoints are found in Section [5](#).

Weekly Time Definitions:

	Regardless the day of Day 15 GC	Day 15 GC is at day 14	Day 15 GC is at day 15	Day 15 GC is at day 16	Day 15 GC is at day 17
Baseline	Day -7 to -1				
Week 1	Day 1 to 7				
Week 2		Day 8 to 13	Day 8 to 14	Day 8 to 15	Day 8 to 16
Week 3		Day 14 to 21	Day 15 to 21	Day 16 to 21	Day 17 to 21
Week 4	Day 22 to 28				
Week 5	Day 29 to 35				
Week 6	Day 36 to 42				

In addition, the change from baseline in CDSD Nausea score and vomiting frequency for Day 15, 3-day average and 7-day average (weekly average) score, will be summarized as stated above, and analyzed within placebo and KAN treatment, evaluating the paired difference from baseline using the Wilcoxon Signed-rank test. The Mann-Whitney U test (Wilcoxon Rank Sum test) will be used to test the difference in the change from baseline for placebo vs KAN-101. The median difference between treatment groups estimated by the Hodges–Lehmann method along with the 95% CI will be reported as well.

Line plots by treatment group will be provided for LSM 95% CI).

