Appendix 1. Summary of Efficacy/Exploratory Analyses

Endpoint	Analysis Type	Population	Analysis Model
Change from baseline in Vh:Cd ratio at Day 29	Summary	FAS	N/A
	Main analysis	FAS	ANCOVA with terms treatment, baseline
	Sensitivity/supplementary analysis	PPS, SAS	ANCOVA with terms treatment, baseline
GC IL-2 (log-transformed) change from Day 15 pre-GC to Day 15 post GC	Summary	BAS	N/A
	Analysis	BAS	ANCOVA with terms treatment, baseline
	Sensitivity/supplementary analysis	PPS, SAS	ANCOVA with terms treatment, baseline
Changes from baseline in IEL density in duodenum biopsy after 2-week GC (at Day 29)	Summary	FAS	N/A
	Analysis	FAS	ANCOVA with terms treatment, baseline
	Sensitivity/supplementary analysis	PPS, SAS	ANCOVA with terms treatment, baseline

Endpoint	Analysis Type	Population	Analysis Model
CDSD change from baseline at each timepoint	Summary	FAS	N/A
	Analysis	FAS	ANCOVA with terms treatment, baseline
	Sensitivity/supplementary analysis	PPS, SAS	ANCOVA with terms treatment, baseline
CDSD 1-Day, 3-Day, 7-Day Nausea Score and Vomiting Frequency and change from baseline at each timepoint post-gluten challenge	Summary	FAS	Observed cases
	Analysis	FAS	All data collected will be included regardless of intercurrent events. Missing data will not be imputed. Wilcoxon Signed-rank test for change from baseline within each group
	Analysis	FAS	All data collected will be included regardless of intercurrent events. Missing data will not be imputed. Mann-Whitney U test (Wilcoxon)

Endpoint	Analysis Type	Population	Analysis Model
			Rank Sum test) for comparison of placebo vs KAN group for change from baseline
PGIS change from baseline at each timepoint	Summary	FAS	N/A
	Analysis	FAS	ANCOVA with terms treatment, baseline
PGIC at each timepoint	Summary	FAS	N/A
	Analysis	FAS	ANOVA with term treatment
Marsh- Oberhuber score	Summary	FAS, PPS, SAS	N/A

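### Each week's CDSD score is compared by its own observed-case ANCOVA, so a participant whose Week 4 diary is missing drops out of that comparison and the Week 3 score is not used

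*SAP*

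**What the plan says.** SAP Section 5.3.2 sends the weekly CDSD changes to the general model: the item averages, the Total Score "and the weekly average CDSD GI Domain Score will be analyzed using ANCOVA models in" Section 4.2.1, where "the change from baseline will be analyzed by timepoint using analysis of covariance (ANCOVA) model with treatment as a factor, baseline as a covariate". Neither section has a repeated-measures term or uses an earlier post-baseline week.

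On missing data, SAP Section 4.3 states "Other missing values will not be imputed for safety, efficacy and PK endpoints", and Protocol Section 9.4.1.2 has "No imputation for missing efficacy and safety data". SAP Section 2.3 defines when a week is lost: "If daily scores are missing for more than half of total days in a specific week, the average score is missing for that week".

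The main analysis set for the patient-reported outcomes is the FAS, whose members "receive all 3 doses of study intervention, and complete at least 7 days of the 2-week GC without prohibited medications". The Section 5 table row that begins "PRO (CDS, PGIS, PGIC" gives N/A for sensitivity sets. The Appendix 1 row "CDSD change from baseline at each timepoint" lists the Per Protocol Set and the Safety Analysis Set (SAS), with the same ANCOVA.

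**The concern.** A FAS member has at least seven GC days and fills in the diary daily (Protocol Section 8.2.3.1), so a Week 3 score normally exists. If that person's Week 4 score is missing, the Week 4 ANCOVA drops the person, and nothing in the model carries over what Week 3 showed. The comparison is unbiased only if, given treatment and baseline, missing Week 4 is unrelated to the Week 4 score. In a gluten challenge with expected gastrointestinal symptoms, people with a bad Week 3 may well be the ones who leave. If that happens more on placebo, the remaining placebo participants look better than the whole arm would have, and the treatment difference shrinks.

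Symptoms before and during the challenge are a stated exploratory objective, and Week 4 (Days 22 to 28) is the second of the two challenge weeks.

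**Working it through.** **1. Figures in the plan.** There is no CDSD effect size, SD, between-week correlation or rate of loss after Week 3. The only dropout figure, in Protocol Section 9.6, concerns Vh:Cd. It reproduces by noncentral t with difference 0.5, SD 0.5 and two-sided 5%: 26 per arm gives 94.2% (stated 94%), and 20.8 against 15.6 evaluable gives 82.7% (stated 82%). It says nothing about CDSD.

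**2. Who loses Week 4.** Week 4 has seven days, so four missing days lose it and four entries keep it. With GC from Day 15, the seventh GC day is Day 21. With daily entries, Week 4 is lost only if the last entry falls on about Days 21 to 24; a last entry on Day 25 leaves Days 22 to 25, which is four. With GC from Day 17 the seventh GC day is Day 23, so the window is shorter still. A participant who stays but skips most Week 4 entries is lost too.

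**3. Size of the bias (assumed inputs).** Take residual SD 1 in each week, correlation ρ between weeks, baseline slope 0.5 with baseline SD 1, and removal of the fraction q with the worst Week 3 scores in each arm. With z the upper q point of the normal distribution, k(q) = φ(z)/(1 − q), and the Week 4 difference falls short by about

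ρ × [k(q placebo) − k(q KAN-101)] / √1.25.

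| Loss, KAN-101 v placebo | k(placebo) − k(KAN-101) | Shortfall, ρ = 0.5 | Shortfall, ρ = 0.8 | As % of 0.70 SD |
|---|---|---|---|---|
| 4% v 8% | 0.162 − 0.090 = 0.072 | 0.03 | 0.05 | 5% to 7% |
| 4% v 12% | 0.227 − 0.090 = 0.137 | 0.06 | 0.10 | 9% to 14% |
| 20% v 40% | 0.644 − 0.350 = 0.294 | 0.13 | 0.21 | 19% to 30% |
| 20% v 20% | 0 | 0 | 0 | 0% |

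This is the strict case, in which the Week 3 score alone decides who leaves. A looser link gives less. A simulation with true difference 0.70 and loss of 4% v 8% to 6% v 14% gave 0.63 to 0.68, an attenuation of about 2% to 10%.

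**4. Simulation check.** 26 per arm, true Week 4 difference 0.50 SD, 2,000 runs per row. The likelihood estimate uses Week 3 as a mixed model would.

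| Leavers of 26, placebo v KAN-101 | ρ | Leaving depends on | Per-week ANCOVA | Likelihood with Week 3 | No data missing |
|---|---|---|---|---|---|
| 3 v 1 | 0.5 | Week 3, strictly | 0.445 | 0.506 | 0.502 |
| 3 v 1 | 0.8 | Week 3, strictly | 0.394 | 0.494 | 0.496 |
| 3 v 1 | 0.8 | Week 3, loosely | 0.446 | 0.503 | 0.504 |
| 10 v 5 | 0.5 | Week 3, strictly | 0.378 | 0.517 | 0.518 |
| 10 v 5 | 0.8 | Week 3, strictly | 0.295 | 0.510 | 0.506 |
| 10 v 5 | 0.8 | Week 3, loosely | 0.335 | 0.492 | 0.493 |
| 10 v 5 | 0.8 | nothing (random) | 0.510 | 0.511 | 0.510 |

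The shortfalls match the formula: 0.496 − 0.394 = 0.102 for 3 v 1, and 0.506 − 0.295 = 0.211 for 10 v 5. In SD units they do not depend on the true effect. With a true effect of zero and 10 v 5 leavers under a loose link, the ANCOVA showed a false disadvantage for KAN-101 of 0.10 to 0.15 SD. The likelihood estimate had a root mean squared error no higher than the ANCOVA in every setting tried, including random and equal loss.

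**The case against.** Much of the case for leaving the plan alone stands.

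- A reader might take the 20% and 40% dropout in Protocol Section 9.6 as the expected loss here. The documents do not support that. The scenario is about people without the primary assessment, and it equates those evaluable with the FAS. Someone who leaves after seven GC days has the biopsy at the early termination visit (Protocol Section 8.2.1), and SAP Table 7 accepts Days 22 to 43. The 20% and 40% therefore mainly describe people outside the FAS, who are absent from every CDSD week. The 20% v 40% rows above are an extreme, not a forecast.
- A reader might infer that Week 4 compares only those who tolerated gluten. It does not. Protocol Section 8.2.1 lets a participant with at least seven GC days continue to Day 29, and that person's diary counts even if gluten was stopped. Weeks 5 and 6 follow the challenge.
- The loss window is only a few days, and the bias needs loss that is both symptom-driven and unequal between arms.
- The endpoint is exploratory and has no estimand. Protocol Section 9.4.4 allows its results to be left out of the study report. Week 3 itself is analysed, as are Day 15 and 3-day nausea and vomiting scores.
- An unstructured model over six weeks has 6 × 7 / 2 = 21 covariance parameters with about 52 participants, and may not converge for all seven outcomes. The simulation tested two weeks, not six.

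These points limit the size and importance of the problem. They do not remove it: data already collected are unused, and the alternative was no worse in any setting tried.

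**Conclusion.** The concern holds as a cheap improvement. The plan's per-week ANCOVA discards Week 3 information for FAS members without a Week 4 score. The Week 4 difference is biased toward no effect if their loss follows Week 3 symptoms and is more frequent on placebo. With a true difference of 0.70 SD and correlation 0.5 to 0.8, the attenuation is about 2% to 14% at 4% v 8% to 12% loss and at most about 30% at 20% v 40%. It is nil under random loss, or under equal loss with the same mechanism in both arms. All of these inputs are assumptions, and given the short window the lower range is the more realistic. The primary Vh:Cd conclusion is not touched.

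**What to change.** Analyse the weekly averages of CDSD Total, GI domain and the five severity items with one mixed model for repeated measures per outcome: treatment, week, treatment × week, baseline, baseline × week; unstructured covariance, with a simpler structure named in advance in case it does not converge; Kenward-Roger degrees of freedom. Report the same weekly LSM differences and confidence intervals. Keep the per-week ANCOVA as supplementary if wanted.

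Fit the same model in the SAS, because a model on the FAS cannot recover participants with fewer than seven GC days. Read it with care: under Protocol Section 7.1, those who do not receive three full doses have no challenge. Reconcile Appendix 1 with the N/A in the Section 5 table.

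The cost is SAP wording and code on the same data. The model assumes missing at random given treatment, baseline and earlier weeks, which is weaker than what the per-week ANCOVA needs but still cannot be tested. The modelling work is slightly greater.

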### **8.2.1. Gluten Challenge**

All eligible, enrolled participants that received all three doses of study intervention will undergo a 2-week GC at starting Day 15.

- Participants are required to fast for at least 6 hours (or overnight), except for water and any medications they might have previously been prescribed, prior to GC. This pertains to both the study clinic visit during which the GC is performed (see [SoA](#)) and the at-home GC.
- At the Day 15 study visit, a qualified staff member will prepare the GC.
- Participants will consume 9g of gluten protein PO in the clinic and the participant will be observed for at least 4 hours to monitor for hyperacute reactions requiring medical treatment and collection of biomarker samples.
- Materials will be sent home with the participant to complete the GC daily for the next 13 days.

Completion of the GC is defined as consumption of the entirety of the 9g GC within approximately 15 minutes.

- At the Day 15 visit, participants will consume the GC on site under the observation of site staff. Participants will complete the remaining days of GC at home and document the completion of the GC via the eDiary.

Compliance with the GC is defined as completion of all 14 days of the GC. Only participants fully compliant with the GC may be analyzed as part of the PPS (see [Section 9.3](#)).

Only participants who have completed at least 7 days of GC should undergo the second EGD with biopsy. For participants who:

- Continue in the study, the EGD with biopsy will take place at the Day 29 visit (see [SoA](#)).
- Discontinue early, the EGD with biopsy will take place at the ET visit (see [SoA](#)).

Any symptoms associated with the GC should be recorded as AEs (see [Section 8.4](#)). Any AEs associated with the GC study assessment are separate to AEs related to study intervention (KAN-101/placebo).

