#### **8.2.3.1. CDSD v2.1**

The CDSD v2.1, a novel patient-reported outcome measure developed for use with participants with CeD, consists of five symptoms including diarrhea, abdominal pain, bloating, nausea, and tiredness. The CDSD v2.1 assesses severity, in five scales from “none” to “very severe”, and frequency. The CDSD v2.1 will be assessed daily as part of the eDiary beginning during the screening period after signing the ICD.

The CDSD v2.1 should be completed for at least 7 consecutive days during screening at any time prior to the baseline visit (Day 1). After screening and through the end of the study, compliance with the CDSD v2.1 is defined as 80% completion.

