Table 7 Analysis Windows for biopsy endpoints (Vh:Cd ratio, IEL density, Marsh-Oberhuber score)

Visit Label	Targeted Day	Analysis window for data sets
Baseline (Screening up to first dosing)	Day 1 pre-dosing	Last observation prior to first dosing date
Day 29	Day 29	Day 22 – Day 43

Table 8 Analysis Windows for IL-2 and CDSD at Day 15 (first GC Day)

Visit Label	Targeted Day	Analysis window for data sets
Day 15	Day 15	The first GC day, Day 14 – Day 17

[figure not shown]

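### On the first gluten-challenge day, the SAP's earliest-record rule for the CDSD can select an entry made before the gluten as the Day 15 nausea and vomiting value

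*SAP*

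**What the plan says.** SAP 5.3.2 sets the rule for several diary entries on one day: "If there are multiple records on a same day, the earliest one will be used for analysis". It applies to every study day.

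SAP 2.3 makes the first GC day an outcome of its own: "Day 15 Nausea score and vomiting frequency will be analyzed as well". SAP 5.3.2 then compares change from baseline in that value within arms (signed-rank test) and between arms (rank-sum test with a Hodges–Lehmann estimate). The Appendix 1 row for these outcomes reads "CDSD 1-Day, 3-Day, 7-Day Nausea Score and Vomiting Frequency and change from baseline at each timepoint post-gluten challenge".

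The CDSD window for Day 15 in SAP Table 8 is "The first GC day, Day 14 – Day 17". It gives no clock time and does not require the record to follow the GC.

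On collection, Protocol 8.2.3.1 says: "The CDSD v2.1 will be assessed daily as part of the eDiary beginning during the screening period after signing the ICD". It sets neither a time of day nor an order relative to the GC. Protocol 8.2.1 places the first GC at a clinic visit: "At the Day 15 visit, participants will consume the GC on site under the observation of site staff".

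**The concern.** The Day 15 value is meant to describe how the participant felt after gluten. An entry completed before the gluten was eaten cannot do that. When two entries on that day fall either side of the GC, the rule keeps the one that cannot carry the information and sets aside the one that can.

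What is at stake is the 1-day nausea and vomiting comparison. Each pre-GC value kept in place of a reaction moves that participant towards no change. If this happens to a similar extent in both arms, it understates the within-arm change and shrinks the KAN-101 versus placebo difference.

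**Working it through.** The plan gives no figure that depends on this rule, so there is nothing to reproduce. The check has three parts.

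**1. Does anything in the visible text prevent the problem?**

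- The general tie rule in SAP Appendix 2.1 takes the value closest to the targeted day. It cannot separate two records on the same day.
- Table 8 works by calendar day.
- SAP Tables 4 and 5 do split the first GC day into before and after the GC, for vital signs and laboratory tests. The protocol's Schedule of Activities does the same for IL-2. There is no such split for the CDSD.
- SAP Appendix 2.2, where the diary would appear, shows only a copyright notice. Its recall period and any completion instruction cannot be checked.

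Nothing visible prevents the problem.

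**2. Effect on one participant.** Assume 0–4 coding (five severity levels, Protocol 8.2.3.1), pre-GC nausea 0 and post-GC nausea 4. Keeping the pre-GC record lowers:

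- the Day 15 value by 4 − 0 = 4;
- the first 3-day average, which starts on the GC day (SAP 2.3), by 4/3 = 1.33;
- the Week 3 average in the 5.3.2 table, which includes the GC day, by 4/7 = 0.57 when the GC is on Day 15. The range is 4/8 = 0.50 (GC on Day 14, Days 14–21) to 4/5 = 0.80 (GC on Day 17, Days 17–21).

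SAP 2.3 starts Week 3 on the day after the GC. Under that definition Week 3 is not affected, so the two sections disagree.

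**3. Effect on the comparison.** Let μP and μK be the mean post-GC scores in the placebo and KAN-101 arms, μ0 the mean pre-GC score, and q the share in each arm whose earliest record that day is pre-GC and is followed by a post-GC record. Assume that q and μ0 are the same in both arms and that being affected is unrelated to the score. Then

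[(1 − q)μP + qμ0] − [(1 − q)μK + qμ0] = (1 − q)(μP − μK).

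Power needs assumed score distributions (percentages at scores 0 to 4). Two sets were simulated with 26 per arm and a two-sided 5% rank-sum test. Pre-GC scores were 85/10/5/0/0 in both sets (mean 0.2).

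- Set A: placebo 30/15/20/20/15 (mean 1.75), KAN-101 60/15/12/8/5 (mean 0.83), difference 0.92.
- Set B: placebo 20/15/20/25/20 (mean 2.1), KAN-101 50/20/15/10/5 (mean 1.0), difference 1.1.

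| q | Participants per arm (26q) | A: difference | A: power | B: difference | B: power |
|---|---|---|---|---|---|
| 0 | 0 | 0.92 | 69% | 1.1 | 82% |
| 2% | 0.5 | 0.90 | 66% | – | – |
| 5% | 1.3 | 0.87 | 63% | – | – |
| 10% | 2.6 | 0.83 | 59% | 0.99 | 71% |
| 25% | 6.5 | 0.69 | 46% | 0.83 | 53% |
| 50% | 13 | 0.46 | 24% | 0.55 | 28% |

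The differences follow the formula. The power figures carry simulation error of about a percentage point and depend heavily on the assumed distributions: with no affected participants the two sets already differ by 13 points.

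**The case against.** The strongest reply is that the trigger is narrow. The diary is a once-daily instrument, so a second record on the same day is an exception. Harm needs two records that fall either side of the GC on one particular day. At 2% to 5%, about one participant per arm or fewer, the loss in the table is slight. This stands: the documents give no basis for a large q, and the lower rows should not be read as forecasts.

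The recall period is also unseen. With a look-back question, the next day's entry might pick up part of the reaction. That too stands, but a record completed before the GC still cannot report a reaction to it.

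A reader might infer that the acute reaction is lost to the trial. The documents do not support that. Protocol 8.2.1 has GC symptoms recorded as adverse events, SAP 5.5.1 summarises GC-related events separately, and later diary days still feed the 3-day and weekly averages. Protocol 9.4.4 treats these outcomes as exploratory and for internal use.

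A reader might also infer that every at-home GC day needs correcting, by taking the latest record. The text does not support this either. The only separate 1-day analysis is of the first GC day. Participants who feel ill may be more likely to make a second entry, so a latest-record rule could favour symptom-driven reports, while baseline would still use the earliest record.

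Finally, the contrast with Tables 4 and 5 is only partly apt, because those are site measurements. Table 3 windows two other patient-reported measures, PGIS and PGIC, by day without a split. But Appendix 1 does not label those as post-gluten challenge, so the mismatch is specific to the nausea and vomiting values.

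**Conclusion.** The point holds in a limited form. Where entries fall either side of the first GC, the stated rule selects a record that contradicts the SAP's own post-gluten label for that outcome. The expected Day 15 difference is then reduced to about (1 − q) of its size. That result rests on q and the pre-GC scores being alike in both arms and on re-entry being unrelated to symptoms; if those who react are the ones who re-enter, the loss could be larger for the same q. The documents give no value for q, and it may be small.

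The effect is confined to the exploratory Day 15 nausea and vomiting comparison and, in part, to the averages that include that day. The primary endpoint (Vh:Cd) and the secondary IL-2 and IEL endpoints do not use the diary. The appropriate weight is a change to consider.

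**What to change.** In SAP 5.3.2 and Table 8, state that for the 1-day Day 15 nausea and vomiting analysis:

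- only a record time-stamped after completion of the first GC is eligible;
- if there are several such records, the earliest is used;
- if there is none, the value is missing.

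Keep the earliest-record rule on all other days, and repeat the Day 15 analysis under it as a sensitivity analysis. In the same edit, say which Day 15 value enters the first 3-day average, and reconcile the start of Week 3 between SAP 2.3 and the 5.3.2 table.

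The cost is a few lines of SAP text and a comparison of times. The existing rule already presupposes that records within a day can be ordered, and the 4-hour post-GC blood sample requires the site to know when the first GC was completed. That diary entries carry usable time stamps is an assumption to confirm. The downside is that a few Day 15 values become missing, including those of participants whose only entry that day was made before the GC. A record made soon after the GC may also precede the peak of symptoms. The change should be made before unblinding.
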